## **8. ASSESSMENT OF SAFETY**

### **8.1 Definition of an Adverse Event & Serious Adverse Event**

An adverse event (AE) is any untoward medical occurrence (e.g. any unfavourable and unintended sign, including an abnormal laboratory finding, symptom, or new or exacerbated disease) in a study participant, temporally associated with the use of an investigational product, whether or not it is considered related to the investigational product. A serious adverse event (SAE) is any untoward medical occurrence that results in death; is life threatening; requires hospitalisation or prolongation of an existing hospitalization; or results in persistent or significant disability/incapacity.

*Any event, side effect, or other medical occurrence that is anticipated because of the normal course of treatment (standard care) is not considered an adverse event.*

### **8.2 Relation to the study intervention**

The proposed intervention does not have any known side effects or likely adverse events. There is a small possibility that participants might experience distress as they answer study questions relating to their symptoms, disease, or experience of care. While the research team is not expecting any distress caused specifically by this research, if a participant does suffer distress as a result of this trial, we will refer them to the relevant clinical team at their treating centre for appropriate action. We will also provide information on the free, confidential telephone information and support service run by the Cancer Councils in each state and territory ([contact]).

### **8.3 Recording and reporting of adverse events**

AEs and SAEs will generally be clinical in nature and resolved according to usual medical procedures.

#### **8.3.1 Study sites**

All reported and observed AEs or SAEs that occur during the study must be recorded in the participant's case report form (CRF) and summarised on an AE log that will be reviewed by the site PI every 3 months. If necessary, they must also be notified to the participant's treating oncologist and/or GP (most information about AEs/SAEs will come from the clinician to study staff so notification will not be necessary).

SAEs and AEs potentially related to the intervention must also be reported to the Coordinating PI (or delegate) within 24 hours of becoming aware of the event.

It is the responsibility of the research team member who is initially made aware of the AE/SAE to complete the CRF and AE log, and, for events potentially related to the intervention, to report the information to the Coordinating PI.

#### **8.3.2 Coordinating PI**

The Coordinating PI will report all SAEs possibly related to the intervention to the Sponsor within 24 hours of first becoming aware of the event.

All AEs possibly related to the intervention must be reported to the Sponsor in a line listing at least every 3 months. On conclusion of data collection, a line listing of all AEs will be provided to the Sponsor.

#### **8.4 Follow-up of adverse events and serious adverse events**

Any AEs or SAEs potentially related to the intervention will be followed until resolution or the condition stabilises. The participant's oncologist and/or GP will be kept informed of the outcome of any follow-up for adverse events potentially related to the intervention. All other AEs and SAEs will be followed up by the participant's clinical team according to usual clinical care at that site.

## **9. STUDY OVERSIGHT AND MONITORING**

Study oversight will be provided by the PROMISE Management Group which comprises the Chief Investigators who collectively have skills in managing large-scale research studies, clinical trials, clinical medicine, nursing and allied health, and consumer representatives.

The PROMISE Project Manager will conduct regular site visits to monitor the conduct of the study and will report back to the Principal Investigator and the PROMISE Management Group.

### **9.1 Curriculum Vitae**

All Investigators signing the Protocol and all trial staff will provide a current, signed and dated Curriculum Vitae including name, title, occupation, education, research experience and present and former positions (AppendixE). A Staff Signature List is required.

## 10. **STATISTICAL CONSIDERATIONS**

### 10.1 **Study Hypotheses**

We hypothesise that, compared to usual care, routine self-reporting of e-PROMs will result in:

1. Primary Outcomes:
  - Fewer emergency presentations/unplanned hospital admissions;
  - Better physical and functional well-being at 6 months;
2. Secondary Outcomes:
  - Higher rates of treatment completion;
  - Better health-related quality of life (HRQOL);
  - Lower rates of distress;
  - Lower symptom burden;
  - Fewer out-patient visits;
3. Exploratory Outcomes:
  - A better patient care experience;
  - Better survival;
  - Lower rates of distress and unmet supportive care needs among partners/carers.

We also hypothesise that use of the e-PROM tools will be cost-effective compared to usual care.

### 10.2 **Sample Size Considerations**

Our sample-size has been calculated to achieve a minimum 80% power ( $\alpha=0.05$ ) for our primary outcomes.

- Emergency presentations (measured from linked data that will be close to complete): Previous studies have reported reductions of 17-30% ([9] and personal communication). Assuming a similar baseline rate (1.09/person-year), we require 242 participants per group to detect a 20% reduction with 18 months follow-up.

- HR-QOL: To detect minimally-important differences (where there is no defined minimally-important difference we have used 0.5 standard deviations as recommended [32] we require 70-150 patients per group depending on the outcome. A sample of 200 per group will give >90% power for the primary outcomes in the full population and ~80% power for analyses stratified by e-PROM tool.

Allowing for up to 30% drop-outs (death or withdrawal), we will recruit a minimum of 572 participants (286 per group). We estimate that more than 2000 eligible patients will attend the study hospitals during a 12-month period (data from the Queensland Oncology Analysis System) thus this target is feasible.

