## 5. **STUDY INTERVENTION**

### 5.1 **Intervention**

The full PROMISE intervention combines the e-PROM tools that participants will complete (5.1.1 and 5.1.2) and the associated implementation strategies (5.1.3). The e-PROM tools use validated instruments (DT and ESAS) that have been used in previous studies, are currently being used in the PROMPTCare system in New South Wales [27-29] and are recommended for use nationally by the Cancer Survivorship Group of the Clinical Oncology Society of Australia (COSA).

In addition to their usual care (Section 5.2), participants randomised to the intervention will be oriented to the use of the e-PROM tool (*My Health My Way* at PAH, TVH; *AboutMe* at RBWH, GCH) at their first treatment visit post-randomisation. A reminder service built into the e-PROM systems will prompt participants to complete the tool 48-72 hours before each subsequent clinic visit (for treatment or follow-up), as previous reports identify this as a feasible time frame for health services to action e-PROM data entered [30]. Participants will also be encouraged to complete the tool monthly between clinic visits to monitor their own progress and facilitate early detection of new problems or exacerbation of existing problems.

When participants arrive for their appointment, the site nurse will check the summary report, to ensure the tool has been completed and, if not, they will help the participant to complete it prior to seeing their clinician. Where feasible, they will give the participant a print-out of the report to take in when they see their clinician; the clinician will also be able to access the report electronically. The report will detail the most recent symptoms entered and their severity (severe, moderate, normal/mild according to standard cut-points) as well as trends over time. Hospital-specific protocols (co-designed with clinical staff – see Section 5.3) will also be used to generate a summary patient-risk profile (e.g. urgent, high, medium, low [30]) and provide recommendations for review/referral. Clinicians will then decide on and prioritise management according to individual patient need.

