### 10.3.1 *Primary Outcomes*

**Fewer emergency presentations/unplanned hospital admissions:** we will use Poisson regression to calculate and compare the rate of unplanned hospital presentations (per 10,000 patient days) during follow-up in each group.

**Better physical and functional wellbeing:** we will calculate FACT-G physical and functional wellbeing scores at each time point. If there are missing items, subscale scores will be prorated as per the FACT-G scoring manual. We will compare mean scores in the two groups at 6 months using t-tests followed by general linear models to incorporate baseline covariates, including site, e-PROM tool, type of cancer, type of treatment (e.g. radio or chemotherapy). A difference of 0.5 standard deviations on each scale is considered clinically meaningful.

Differences at other time-points will also be assessed and we will explore changes over time and differences between treatment arms using a multilevel repeated measures model. The model for each post-randomisation point will be adjusted for baseline score and stratification factors.

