### 10.3.3 *Exploratory Outcomes*

**Survival:** we will calculate and the mortality rate (per person-year) in each group and use Cox proportional hazards regression to compare mortality in the two study groups.

**A better patient care experience:** the AHPEQS asks patients to rate 9 aspects of care on a 5-point scale from never (worst) to always (best) and their overall care from very poor to very good. We will use chi-squared tests to compare the proportions of participants in each group that answer mostly or always to each individual item (or good/very good to overall care) and t-tests to compare the mean number of items rated as mostly/always. We will also

compare the proportions of participants who report experiencing physical and/or emotional distress and, among those who report distress, the proportions who reported that healthcare staff discussed this with them.

**Partner/Carer distress and unmet supportive-care needs:** HADs data from carers will be analysed as for participants (above). Analyses of supportive-care needs will compare the frequency of individual needs and specific domains (information needs, healthcare needs, psychological and emotional needs, social and work needs). Parametric and non-parametric tests, as appropriate, will be used to compare the intervention and control groups.

**Sub-group analyses:** We will repeat the primary and secondary analyses above for sub-groups of participants defined by (i) study site, (ii) e-PROM tool (*My Health My Way* vs. *AboutMe*), (iii) cancer type (high vs. low mortality), (iv) type of treatment (curative/palliative), (v) sex, and (vi) computer literacy. This is to examine effect modification and identify scenarios where e-PROM tools are potentially most effective and those where their effectiveness could be improved. We recognise that statistical power will be more limited for some of these stratified comparisons.

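### Section 10.2 gives ~80% power within each e-PROM tool without naming an outcome; it holds only for HR-QOL outcomes needing about 100 or fewer per group, and not for emergency presentations

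*Protocol*

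**What the plan says.** Section 10.2 sets the general target: "Our sample-size has been calculated to achieve a minimum 80% power" at alpha 0.05 for the primary outcomes. It then has two bullets.

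- **Emergency presentations:** from a baseline of 1.09 per person-year, "we require 242 participants per group to detect a 20% reduction with 18 months follow-up".
- **HR-QOL:** the target is the minimally important difference and, "where there is no defined minimally-important difference we have used 0.5 standard deviations as recommended". On that basis, "we require 70-150 patients per group depending on the outcome". The same bullet adds that 200 per group will "give >90% power for the primary outcomes in the full population and ~80% power for analyses stratified by e-PROM tool".

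Section 10.2 then allows for 30% drop-out and recruits 286 per group. Section 5.1 places My Health My Way "at PAH, TVH; *AboutMe* at RBWH, GCH", so each tool runs at two of the four hospitals. Section 10.3.1 says of the primary FACT-G scales: "A difference of 0.5 standard deviations on each scale is considered clinically meaningful". In section 10.3.3 the sub-group plan reads "We will repeat the primary and secondary analyses above for sub-groups of participants", with e-PROM tool as one of the defining factors. It adds that power will be more limited for some of these comparisons.

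**The concern.** The HR-QOL bullet gives a range of requirements that runs above 100 per group. It then quotes one power figure for strata that hold about 100 per arm. An outcome that needs 150 per group for 80% power cannot have about 80% with 100.

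The sentence also speaks of the primary outcomes without restriction. One of the two primary outcomes is emergency presentations, for which the plan itself asks for 242 per group.

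What is at stake is how the tool-specific results are read. Section 10.3.3 wants them to show where the tools work best and where they could be improved. If a reader believes power was about 80%, a non-significant result for one platform looks like fair evidence against that platform. At 63% power a real effect of the assumed size is missed more than one time in three. At 44-48% it is missed slightly more often than not.

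**Working it through.** **Inputs**

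- Alpha 0.05 (10.2). Sidedness is not stated, so two-sided is assumed.
- HR-QOL requirement 70-150 per group (10.2), read as the requirement at 80% power.
- 0.5 SD as the meaningful difference (10.2 and 10.3.1).
- 200 per group analysed and 286 recruited (10.2): 200/0.7 = 286, which reproduces.
- Site targets 150-175 at PAH and RBWH, 110-145 at GCH and TVH (3.3), read as per site because the total of 572 requires it. Each tool has one larger and one smaller site, so 260-320 participants, or 130-160 per arm before losses.
- An even split of 572 gives 143 per arm per tool. After 30% losses this is 100.

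**HR-QOL**

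If an outcome needs n0 per group for 80% power, then d = (1.960 + 0.842) × √(2/n0). Power with m per arm is Φ(2.802 × √(m/n0) − 1.960).

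The plan's full-population figure comes first, with m = 200. Power is 89.9% for n0 = 150, 97.7% for n0 = 100, 99.7% for n0 = 70, and 99.9% at 0.5 SD. The printed >90% reproduces for HR-QOL, within rounding at the top of the range.

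Within one tool, m = 100:

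| Outcome | d | Power |
|---|---|---|
| needs 150 per group | 0.32 | Φ(0.33) = 63% |
| needs 100 per group | 0.40 | Φ(0.84) = 80% |
| needs 70 per group | 0.47 | Φ(1.39) = 92% |
| 0.5 SD directly | 0.50 | Φ(1.58) = 94% |

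A figure of 78-82% requires an outcome needing about 95-105 per group. The range allows for such an outcome, but none is named.

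Variants:

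- One-sided test: 65% for n0 = 150 and 91% for n0 = 70.
- 70-150 read as the requirement at 90% power (replace 2.802 by 1.960 + 1.282 = 3.242): 75% for n0 = 150 and 97% for n0 = 70.
- 143 per arm, no losses: 78% for n0 = 150. This sets aside both the 200 per group and the 30% drop-out in the plan.

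**Emergency presentations**

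Expected events per person over 18 months are 1.09 × 1.5 = 1.635 under usual care and 1.308 after a 20% reduction. The variance term is 1/1.635 + 1/1.308 = 1.376, and ln 0.8 = −0.2231.

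The plan's figure first: n = 2.802² × 1.376 / 0.2231² = 217 per group. The printed 242 is somewhat larger. An unstated allowance of about 10% would explain it (217/0.9 = 241), and it is conservative, so it is not at issue here.

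Power with m per arm is Φ(0.2231/√(1.376/m) − 1.960). The alternative takes the plan's 242 as giving exactly 80%: Φ(2.802 × √(m/242) − 1.960).

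| Per arm | Plain Poisson | Scaled from 242 |
|---|---|---|
| 100 (one tool, after 30% losses) | 48% | 44% |
| 143 (one tool, no losses) | 62% | 58% |
| 160 (one tool, top of site targets, no losses) | 67% | 62.5% |
| 200 (full population, as in the HR-QOL bullet) | 77% | 72% |

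With 24 months of follow-up, for which section 3.4 says funding is not yet secured, the means are 2.18 and 1.744, and 143 per arm gives 75% (plain Poisson). Overdispersion would lower all of these.

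**The case against.** **Scope.** The sentence sits in the HR-QOL bullet and is tied to 200 per group, while presentations have their own bullet with no stated within-tool power. At 200 per group presentations do not reach >90% even in the full population, so the author probably meant the FACT-G scales. This stands in part. The presentation figures do not refute a claim clearly made about presentations; they show that the wording is too broad. It names the primary outcomes without limit, and section 10.3.3 repeats all primary analyses by tool.

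**The main HR-QOL case is fine.** At 0.5 SD, the difference section 10.3.1 names for the primary wellbeing scales, power within a tool is 94%. This stands. A reader might infer that ~80% cannot be obtained from the plan's inputs at all, or that every tool-stratified analysis is underpowered. The documents do not support that: ~80% lies inside the 63-92% range and is met or exceeded wherever about 100 or fewer per group are needed. No outcome is named as needing 150 either, and if the range was set at 90% power the worst case is 75%.

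**Presentations could do better.** A reader might take 62% (143 per arm) as a ceiling. It is not: 160 per arm gives up to 67%. Combining 160 per arm, no losses and 24 months would give about 79% under plain Poisson: Φ(0.2231/√((1/2.18 + 1/1.744)/160) − 1.960). That is neither the 200 per group nor the 18 months on which section 10.2 rests. A 30% reduction, the top of the range section 10.2 cites, would have 83% with 100 per arm, but the plan is sized on 20%.

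**The analyses are exploratory and carry a power caveat.** True, and it limits the harm. Nothing in the protocol says that a null stratum will be read as no effect. But the caveat is generic, whereas section 10.2 singles out the tool strata as having about 80%, so a reader would not apply the caveat to them.

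**Conclusion.** The concern holds in a limited form. The ~80% is not wrong for every outcome; it is printed without the restriction it needs. It is right or conservative for HR-QOL outcomes needing up to about 100 per group. It is about 17 points too high for one needing 150 (63%). For a 20% reduction in presentations over 18 months, within-tool power is about 44-67% depending on how many participants count, 13 to 36 points below 80%. The companion >90% likewise cannot cover presentations at 200 per group (72-77%).

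This rests on a two-sided 0.05 test, an even split between the tools (except the 160-per-arm case), 70-150 read as the requirement at 80% power, and no overdispersion. If 70-150 was set at 90% power, the HR-QOL range is 75-97% and the gap there is small; the result for presentations is unaffected.

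A reader might go further and infer that the trial is too small. That does not follow. The full-population HR-QOL power reproduces, 286 per group exceeds the 242 required for presentations, and the tool strata are exploratory.

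**What to change.** In section 10.2, do one of the following:

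- limit both the >90% and the ~80% to the named HR-QOL outcomes for which they were computed; or
- replace the ~80% with a range by outcome: with about 100 per arm per tool, about 63-92% for HR-QOL outcomes, and about 44-67% for a 20% reduction in presentations over 18 months (100 to 160 per arm). The >90% should still be confined to HR-QOL.

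In either case, add one sentence saying that a non-significant result within one tool is not evidence that the tool is ineffective.

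The cost is a sentence or two and a less favourable stated power for an exploratory analysis. No participants, data or design changes are needed.

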### 10.3 **Statistical Analysis Plan**

Data analysis will be guided by a formal statistical analysis plan that will be finalised prior to any analyses being conducted. All analyses will be intention-to-treat but compliance with the intervention will be assessed and, if there is substantial non-compliance, per-protocol analyses will also be performed. In exploratory sub-group analyses, we will also conduct analyses stratified by e-PROM tool, study site, gender, computer literacy, cancer type and cancer stage (early vs. advanced).

To preserve the blinding during preliminary analyses, the Data Manager will generate datasets with participants' true allocation code replaced by a random dummy code. This will

be replaced by the true code when we perform the final analyses (as in the D-Health trial [26]).

### 10.3.1 *Primary Outcomes*

**Fewer emergency presentations/unplanned hospital admissions:** we will use Poisson regression to calculate and compare the rate of unplanned hospital presentations (per 10,000 patient days) during follow-up in each group.

**Better physical and functional wellbeing:** we will calculate FACT-G physical and functional wellbeing scores at each time point. If there are missing items, subscale scores will be prorated as per the FACT-G scoring manual. We will compare mean scores in the two groups at 6 months using t-tests followed by general linear models to incorporate baseline covariates, including site, e-PROM tool, type of cancer, type of treatment (e.g. radio or chemotherapy). A difference of 0.5 standard deviations on each scale is considered clinically meaningful.

Differences at other time-points will also be assessed and we will explore changes over time and differences between treatment arms using a multilevel repeated measures model. The model for each post-randomisation point will be adjusted for baseline score and stratification factors.

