### 2.3.1 **Primary outcomes**

- (i) The rate of unplanned hospital presentations/admissions. This information will be obtained from hospital records and linkage to the Queensland Health Admitted Patients Data Collection (QHAPDC), Emergency Data and Medical Benefits Scheme (MBS) data.
- (ii) Physical and functional wellbeing measured by the Physical Wellbeing and Functional Wellbeing subscales of the Functional Assessment of Cancer Treatment – General (FACT-G) scale [15].

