### **4.3 Treatment Assignment Procedures**

#### **4.3.1 *Randomisation Procedures***

Randomisation will be at the patient level, with a 1:1 ratio between groups, using randomly varied permuted blocks, stratified by sex, hospital, treatment intent (curative/palliative) and computer literacy (defined as regular access to a computer/tablet/smart phone and use of email  $\geq 1$ /week vs. less often) as this was shown to be important in previous trials [8, 9]. When a participant completes the Baseline Study Questionnaire, the central web-based database will automatically apply the next relevant record in the allocation sequence, as we have done previously [24-26].

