### 10.3.2 *Secondary Outcomes*

**Higher rates of treatment completion:** we will calculate the fraction of planned primary treatment that participants actually received. We will compare the mean (or median, as appropriate) fraction received and the proportion of participants who received >85% of their planned treatment between the groups using t-tests and chi-squared tests, respectively.

**Better overall HR-QoL, lower rates of distress and lower symptom burden:** we will calculate overall FACT-G (to measure HR-QoL), HADS anxiety and depression (to measure distress) and MSAS (to measure symptom burden) scores at each time point. If there are missing items, subscale scores will be prorated as per the relevant scoring manuals. We will use t-tests to compare the intervention and control groups with respect to absolute levels at each time-point (with 6 months being the primary time-point) and will use mixed effects repeated measures models to assess change over time from baseline. The models for post-randomisation point will be adjusted for baseline score and stratification factors. A difference of 0.5 standard deviations on each scale is considered clinically meaningful.

We will also assess differences in social and emotional wellbeing using these subscales of FACT-G.

**Fewer out-patient visits:** we will use Poisson regression to calculate and compare the rate of unplanned hospital presentations (per 10,000 patient days) during follow-up in each group.

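### Section 10.3.1 fixes Poisson regression for the recurrent-event primary outcome with no allowance for overdispersion, so variation in patients' rates within the randomisation strata would make the p-value and confidence interval too optimistic

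*Protocol*

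**What the plan says.** Protocol section 2.3.1 defines the outcome as "The rate of unplanned hospital presentations/admissions", a rate to which one patient can contribute more than one event. For its analysis, section 10.3.1 states that "we will use Poisson regression to calculate and compare the rate of unplanned hospital presentations (per 10,000 patient days) during follow-up in each group". It names no dispersion parameter, robust variance or patient-level effect for this outcome. Elsewhere the protocol does name methods for repeated data: a multilevel model for the FACT-G scores (10.3.1), mixed models for the secondary scores (10.3.2) and generalised estimating equations for the economic data (10.3.6).

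Under out-patient visits, section 10.3.2 again says "we will use Poisson regression to calculate and compare the rate of unplanned hospital presentations".

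The sizing in section 10.2 opens with "Our sample-size has been calculated to achieve a minimum 80% power", takes its control rate from earlier work ("Assuming a similar baseline rate (1.09/person-year") and concludes "we require 242 participants per group to detect a 20% reduction with 18 months follow-up". It gives no dispersion value. Section 4.3.1 randomises individual patients "with a 1:1 ratio between groups", "stratified by sex, hospital, treatment intent (curative/palliative) and computer literacy". Section 10.3 refers to a separate statistical analysis plan, which is not at hand.

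**The concern.** The Poisson variance is correct only if, given the covariates in the model, every patient has the same underlying rate and repeat visits occur independently. Eligibility (sections 3.2 and 4.1.1) is open to any invasive solid cancer and to systemic or radiation treatment. Cancer type, stage, type of treatment and frailty are not randomisation strata, and one presentation may make another more likely. Each of these pushes the variance of the counts above their mean.

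If that happens, the model-based standard error of the rate ratio is too small. The trial would then be more likely than 5% to report a difference in unplanned presentations where none exists, and its 95% interval would cover the true rate ratio less than 95% of the time. This is one of two primary outcomes. The sample size rests on the same variance assumption, so the power is exposed as well.

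**Working it through.** **Inputs.** Control rate 1.09 per person-year, 18 months, 20% reduction, 80% power, α = 0.05 and 242 per group (section 10.2); 1:1 allocation (section 4.3.1). The sidedness of α is not stated; two-sided is assumed. Full follow-up is assumed throughout. Expected events per control patient: μ = 1.09 × 1.5 = 1.635. Under a 20% reduction: 0.8 × 1.635 = 1.308.

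**The plan's own figure.** With the Poisson variance at the control rate in both arms,

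n = 2 × (1.96 + 0.842)² × 1.635 / (0.2 × 1.635)² = 240 per group,

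or 241 with the t correction, in line with the stated 242. The log rate-ratio formula,

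n = (1.96 + 0.842)² × (1/1.635 + 1/1.308) / (ln 0.8)² = 217 per group,

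is a little smaller. Both set the variance equal to the mean.

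**Overdispersion.** Write the variance as μ + kμ², where k is the dispersion remaining within the randomisation strata. With equal follow-up and no effect, the Poisson standard error is too small by a factor √(1 + kμ). The true type I error of the nominal 5% test is therefore

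2 × [1 − Φ(1.96 / √(1 + 1.635k))].

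With valid standard errors, the log rate-ratio variance term becomes 1/1.635 + 1/1.308 + 2k. The protocol gives no k, so the table shows a range.

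| Residual k | SE too small by | Type I error, Poisson test | Coverage of 95% CI at rate ratio 0.80 | n per group for 80% power, valid SE | Power at 242 | Power at 286 |
|---|---|---|---|---|---|---|
| 0 | 1.00 | 5.0% | 95% | 217 | 84.1% | 89.6% |
| 0.25 | 1.19 | 9.9% | 91% | 296 | 71.7% | 78.7% |
| 0.5 | 1.35 | 14.6% | 86% | 375 | 61.5% | 68.7% |
| 1 | 1.62 | 22.7% | 79% | 533 | 47.2% | 53.7% |

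Simulation of 10,000 null trials with gamma-Poisson counts, 242 per group and no strata gave 9.7%, 14.6% and 23.0% for the Poisson test at k = 0.25, 0.5 and 1. A patient-level robust variance gave 4.9%, 5.1% and 5.5% on the same data.

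**How much dispersion the design tolerates.** On the log rate-ratio formula, 242 per group keeps 80% power only up to k of about 0.08. For scale, an even mix of two patient groups whose rates differ two-fold has relative rates 2/3 and 4/3, so k = (1/3)² = 0.11. With a three-fold difference the relative rates are 0.5 and 1.5, so k = 0.5² = 0.25. These values count as residual k only if the grouping factor is not a randomisation stratum.

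**Effect of the stratification.** Null simulations with 286 per arm and a mean of 1.635, where half the patients have a higher rate and nothing else varies, gave these rejection rates for the Poisson test:

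| Rate difference between the two halves | Simple randomisation | Randomisation stratified on that factor |
|---|---|---|
| two-fold | 7.5% | 4.7% |
| three-fold | 10.4% | 5.1% |
| five-fold | 14.2% | 4.5% |

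Differences between strata therefore do not inflate the test. In the same setting, a robust variance without the strata as covariates rejects only about 2–3% at two- and three-fold differences, which is conservative. When heterogeneity within strata is added, the inflation returns: about 10–12% at residual k = 0.25 and 16–19% at 0.5.

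**The case against.** The strongest reply is that section 10.3.1 names a model family and not a variance estimator. Poisson regression with robust variance is still Poisson regression, and estimator, offset and covariates are details that a statistical analysis plan commonly supplies. Part of this stands. The absence of the strata from the sentence is not a fault in itself, and a rate per patient-day already implies an offset. But the protocol commits a primary outcome to a named model, nothing in it tells the reader that the variance is anything but the model's own, and section 10.2 is built on variance equal to the mean. A later plan that followed the sentence literally could give a wrong p-value.

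The second reply concerns the mechanism. A reader might infer that mixing curative and palliative patients is enough to invalidate the test. The documents do not support that: treatment intent, sex, hospital and computer literacy are all randomisation strata, and the simulations above show no inflation from differences between strata. Only dispersion within strata counts. It is smaller than the total dispersion, and its size is unknown.

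Third, the same criticism might be carried over to GP and specialist visits. Section 10.3.5 only says that those rates will be calculated and compared; it names no Poisson model, so the point does not reach them.

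**Conclusion.** The point holds, conditionally. Section 10.3.1 fixes a model whose standard error is too small whenever patients' rates vary within the randomisation strata or repeat visits cluster, and the protocol contains no safeguard for this outcome. The direction is certain for any positive residual dispersion; the size is not. Across k = 0.25 to 1, a nominal 5% test has about 10% to 23% type I error; at k = 0 it is correct. These figures assume a negative binomial form, a two-sided 5% test and full 18-month follow-up.

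A reader might go further and say that the reported result will be wrong, or that a false claim becomes several times more likely than 5%. The protocol does not support either statement: it gives no dispersion, and at k = 0.25 the error rate is about double the nominal level. What can be said is that a common rate within strata is implausible in a population of mixed tumours and treatments, and that both the analysis and the sample size depend on it.

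**What to change.** In section 10.3.1, specify negative binomial regression, or Poisson regression with patient-level robust variance, for the primary count. Use log days at risk as the offset, include arm and the four randomisation strata as covariates, and report the rate ratio with its 95% confidence interval. The strata belong in the model because an unadjusted robust variance would be conservative under this design.

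Use the same model for the count analysis in section 10.3.2. That sentence stands under out-patient visits but describes unplanned presentations, so its outcome should be reconciled at the same time.

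In section 10.2, state that 242 per group assumes no overdispersion, and restate the power over a range of k, for example the table's figures at 0, 0.25, 0.5 and 1.

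The change needs no new data and only a few sentences of text. The price is a wider interval and a less favourable stated power: changing the analysis protects the p-value and interval but does not restore 80% power. On the same formula even 286 per group with full follow-up falls just short of 80% at k = 0.25.
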